7.1. Semen Samples

The semen parameters (semen count and semen concentration) at baseline and during treatment will represent the mean of two semen samples collected a few days apart at each time point.

In the case of one missing sample at a time point the only sample available will represent the value for that timepoint.

Any sample that was retaken within 2 weeks of the planned sample, due to technical/practical issues, will be included.

7.2. Positive and Negative TB Status

7.2.1. Positive culture

Positive culture refers to the culture being positive for *Mycobacterium tuberculosis* (MTB). The MGIT culture results that are positive with contamination will be considered positive. The MGIT culture results that are contaminated or with no result will be treated as missing. Two sputum samples per visit are collected at each visit throughout treatment and follow-up. The culture result for a given visit is established using all samples obtained for that visit. A positive culture takes precedence over a negative or contaminated culture at the same visit and a negative culture takes precedence over a contaminated culture at the same visit.

7.2.2. Isolated Positive Cultures

It is known that occasionally participants produce sputum samples that are "isolated positives," that is, a positive culture preceded by a series of negative cultures and followed thereafter by at least two negative cultures without an intervening positive result. This phenomenon may be the result of a sealed cavity breaking down or laboratory contamination and does not in itself signify that the participant is relapsing. In the event of a single positive culture result occurring in a participant who has previously been classified as having culture negative status (in the absence of any retreatment), the participant will not be classified as a recurrence unless a second positive culture result is obtained at a separate visit (at least 7 days apart), without an intervening negative culture or unless the participant is lost to follow up or completes the study (and is unable to be brought back) before two negative cultures are obtained. As there is a higher incidence of isolated positives with liquid culture and sometimes even serial "isolated positives", the clinical condition of the participant will also be considered in deciding whether the participant has an unfavourable outcome and re-treatment is indicated.

For example, if a participant after being culture negative has two positive cultures in a row, but is deemed to be doing well clinically, the investigator may choose to leave the participant untreated on clinical grounds. In such a case, so long as two consecutive negative cultures are eventually obtained in the absence of treatment, the participant will not be classified as an unfavourable outcome (defined in §6.1 above).

7.2.3. Culture negative status

Culture negative status is achieved when a participant produces at least two negative culture results at different visits (at least 7 days apart) without an intervening positive culture result for MTB. The date of the first negative culture (date of collection of culture) of these two is the date at which culture negative status was obtained. Once obtained, culture negative status continues until there are two positive cultures at different visits (at least 7 days apart), without an intervening negative culture, or until there is a single positive culture not followed by two negative cultures. Culture negative status can be achieved at any time during treatment or follow-up but before any re-treatment. Culture negative status can be re-established.

Participants with two contaminated or missing samples at a given visit (from month 2 onwards) will be asked to return to produce two more sputum samples.

7.2.4. Inability to produce sputum

In general, inability to produce sputum is treated as being equivalent to having a negative culture result if no other sputum sample is produced at that visit. This includes the rare situation where a participant who never achieves culture negative status due to the inability to produce sputum, after TB has been confirmed on the applicable baseline sample, completes follow-up without clinical or microbiological evidence of relapse. Such participants will be considered to have a favourable outcome and an inability to produce sputum with no other sputum produced at that visit will be treated as a negative culture result.

7.3. Adequate treatment

The definition of adequate treatment sets a limit for the amount of treatment missed. Participants not taking the adequate amount of treatment by this definition will be excluded from the per protocol analyses (PP and TB-PP).

To meet the definition of adequate treatment participants must have taken at least 146 doses (80%) of their allocated 182 day (26 weeks) treatment regimen within 238 days of starting therapy (i.e. 26 weeks plus an allowable 56 day halt (including a maximum of 35 consecutive days) as per the protocol).

7.4. Major protocol deviations for analysis

A major protocol deviation for analysis is a protocol deviation likely to affect to a significant degree the scientific value of the trial and is CSR reportable. These include:

- participants who did not satisfy entry criteria but were entered anyway
- participants who developed withdrawal criteria during the study but were not withdrawn

• participants who received the wrong treatment or incorrect dose

These participants will be excluded from the PP and TB-PP analyses. A list of all major protocol deviations for analysis will be approved by a review committee prior to database lock.

Note: participants attending a long-term outcome visit outside the specified window will be evaluated and considered for potential major protocol violator. Visits within 2 weeks of the window opening will be considered *minor* protocol violators.

7.5. Trial Timings

Date of enrolment is Study Day 1 which is defined as the date on which a participant is administered the first dose of study medication. Other study days are defined relative to the Study Day 1 with Day 2 being the day after Study Day 1 and Day -1 being the day prior to Study Day 1.

For all safety endpoints, baseline is defined as the last non-missing measurement prior to first dose of study treatment unless otherwise stated.

In all analyses, visit date rather than day or week number will be used to define the timing of events.

Assessments should be collected as follows:

- Within ± 3 days of scheduled visit from Day 1 to Week 8
- Within ± 7 days of scheduled visit from Week 12 to Week 26
- Within ± 14 days of scheduled visit during the follow-up phase at or after Week 26 to Week 78

Unscheduled visits will be slotted into windows as appropriate. Scheduled visits falling outside of the defined protocol visit windows will be put into separate visits so that all data, both collected at scheduled and unscheduled time points, are used.

The *treatment period* is defined as a total of 26 weeks from start of therapy.

The *follow-up period* is defined as the period after the end of treatment to the end of follow-up.

7.6. General Statistical Considerations for Analysis

There are three planned analyses that will be performed. The first analysis will be done after all participants have completed the 26 weeks of treatment. The analysis will be on primary outcome data (semen data), secondary reproductive data, culture conversion data up to week 26 and safety data. The second analysis will be done at week 44 and will also be on the semen data available at 44 weeks, secondary reproductive data, culture conversion data to week 44 and safety data. The final analysis will take place after 78 weeks and will include analyses on all data including the TB efficacy analysis as outlined in §6.1.

There will be no specific strategy to deal with missing data i.e. it will not be imputed. A complete case analysis will be performed.

For the safety analysis, if there are multiple assessments in a visit, the highest grade non-missing value within a visit will be used in the summaries, however all will be shown in the listings. If numeric

data is beyond range of lab detectability and result is showed as "<XX" or ">XX" then the numeric XX value will be used for summary statistics.

Baseline is defined as last available measurement prior to dosing and post baseline abnormalities are included in the summary if the subject did not meet the abnormality criteria at baseline or toxicity grade at post baseline is higher than that on baseline.

7.7. Newly notable abnormalities

A newly notable laboratory abnormality is defined as an abnormality observed post baseline that meets the notable criteria shown in Table 1 below and that did not exist at baseline. Participants can still meet the criteria for newly notable laboratory event if the baseline value is missing.

Lab Test Type	Laboratory Variable	SI Units		
Liver	AST	$>$ 3 x ULN and \leq 5 x ULN		
		> 5 x ULN and ≤ 8 x ULN		
		> 8 x ULN		
	ALT	$>$ 3 x ULN and \leq 5 x ULN		
		> 5 x ULN and \leq 8 x ULN		
		> 8 x ULN		
	Total Bilirubin	> 2 x ULN		
	Alkaline Phosphatase (ALP)	> 2 x ULN		
Chemistry Labs	Other:			
	ALT or AST > 3 x ULN and total bilirubin > 2 x ULN			
	ALT or AST > 3 x ULN and total bilirubin > 2 x ULN and ALP <2 x			
	ULN (potential Hy's law case)			
	Lipase	> 2 x ULN to \leq 5 x ULN		
		> 5 x ULN		

Table 1: Notable Criteria for Laboratory Data

8. Analysis Populations and Definitions

8.1. Primary Semen Analysis populations

8.1.1. The intent-to-treat (ITT) population

The primary and secondary semen analyses will be conducted on the ITT population, defined as all participants who at took at least one dose of the study medication. All data available will be considered for each time-point.

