#### ii.Baseline to Week 78, including Early Withdrawal and Unscheduled Visits

TMP-C-SOP01-B V1.0 30-JAN-2019

• Two spot sputum samples taken at least 30 minutes apart will be collected under the coaching and observation of the trial staff.

• If there is an *Mtb* positive culture (after the participant has previously converted to culture negative) at or after the last visit of the treatment period (Week 26), the participant should return for an unscheduled visit(s) to give additional sputum samples a minimum of 7 days after the previous sample, or to document that the participant is not able to produce sputum.

Additional samples may be required to define a participant sputum outcome status.

The following analyses will be performed on these samples:

- Liquid Culture (MGIT) for *Mtb*, followed by an identification test to detect presence or absence of *Mtb* and obtain the time to positivity (TTP) when culture positive and not contaminated will be performed on all samples.
- Susceptibility Testing for bedaquiline (B), moxifloxacin (M), pyrazinamide (Z) and pretomanid (Pa) on the following cultures:
  - The 1st positive non-contaminated *Mtb* positive culture from Screening up to Week 4;
  - On *Mtb* positive cultures, after the participant has previously converted to culture negative at or after the last visit of the treatment period (Week 26);
  - At Early Withdrawal;
  - At Bacteriological failure, which is defined as failing to attain culture negative status at or before the end of treatment (Week 26). The last available positive culture will be used for susceptibility testing e.g., the Early Withdrawal or Week 26 culture of a participant who withdrew and/or started re-treatment before the Week 78 visit or the Week 78 culture of a participant who has not started re-treatment.

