# **Trial Design Rationale**

The primary purpose of this Male Reproductive Safety – "BPaMZ/SEM"- clinical study is to generate data to evaluate the potential effect of once daily 200mg Pretomanid on human testicular function whilst being dosed for 6 months in patients with Drug Resistant (DR-TB) Pulmonary Tuberculosis. The 6 months dosing period covers current use of pretomanid is an approved antimicrobial regimen for the treatment of TB. (Pretomanid in combination regimen with Bedaquiline and Linezolid (BPaL) for people with XDR-TB or treatment-intolerant/non-responsive MDR-TB). It is not feasible to evaluate the potential testicular toxicity of once daily 200mg Pretomanid in this BPaL regime, as Linezolid has shown toxicity on testicular function in non-clinical studies. Therefore, the study will be conducted using the antimicrobial regimen consisting of Bedaguiline (B) plus Pretomanid (Pa) plus Moxifloxacin (M) and Pyrazinamide (Z) (BPaMZ) for 6 months in DR-TB patients. Participants will also be followed up to 18 weeks post dose to evaluate and ensure coverage of potential recovery of semen parameters which encompasses one and one-half cycles (cycle length is around 75 days) of the seminiferous epithelium. This also includes epididymal transit time (since we are sampling and evaluating semen), which adds another  $\sim 10$  days. Thus, in days 75 + 37.5 + 10 = 122.5 days or 17.5 weeks, therefore 18 weeks should be sufficient for follow-up period.

The safety of pretomanid has been tested in 10 single- and multi-dose Phase I studies with healthy adult male and female participants, receiving single oral doses of pretomanid ranging from 50 to 1500 mg and multiple oral doses ranging from 200 to 1000 mg/day given for up to eight days. Pretomanid has also been studied in combination regimens in patients for up to 9 months in Phase 2 and 3 studies. For this study adult male DR-TB patients who can complete the trial will be required.

For assessment of the male reproductive safety profile the following parameters will be evaluated in adult male participants with Drug Resistant (DR-TB) Pulmonary Tuberculosis.

For assessment of the male reproductive safety profile the following parameters will be evaluated.

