- 17. Receiving any form of hormone or hormone-like (nutraceuticals) therapy, except for well treated hypothyroidism.
- 18. Received Pretomanid and/or Delamanid to treat TB.
- 19. Known chronic hepatitis B or C.

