## 6.3 Restrictions

Concomitant medications should be kept to a minimum during the treatment period of the trial. However, if concomitant medications are necessary for the participant's welfare and are unlikely to interfere with the IMP, they may be given at the discretion of the Investigator. For any concomitant medications given as a treatment for a new condition or a worsening of an existing condition occurring after signing of the Informed Consent Form, the condition must be documented on the Adverse Event pages of the electronic Case Report Form (eCRF).

The prescribing information for all concomitant medication should be consulted and reviewed carefully. The determinations listed in the respective contraindicated, warning, and precaution sections must be respected to prevent any potentially serious and/or life-threatening drug interactions.

The following recommendations should be followed with regards to concomitant medication to avoid possible drug interaction with the IMP:

**Moxifloxacin**: The IMP should be taken either 4 hours before or 8 hours after taking the following products:

- An antacid, multivitamin, or other product that has magnesium, aluminium, iron, or zinc
- Sucralfate
- Didanosine

The following medicinal products are prohibited from the Screening visit and during the treatment period:

- Quinolone antimalarial (e.g., chloroquine and quinacrine). Participants who have malaria at screening are to be excluded. However, if a participant develops malaria during the trial, the Investigator is advised to consult the Malaria Treatment Guidance document regarding the interaction between moxifloxacin and bedaquiline with anti-malarial drugs. Investigators may also contact the Sponsor Medical Monitor for further guidance.
- Medicinal products used to treat pulmonary TB: including but not limited to gatifloxacin, amikacin, cycloserine, rifabutin, kanamycin, para-aminosalicylic acid, rifapentine, thioacetazone, capreomycin, other quinolones except moxifloxacin, thioamides, and metronidazole.

The following medicinal products should be avoided from Day 1 (Baseline visit) and during the treatment period as much as possible. Investigators may also contact the Sponsor Medical Monitor for further guidance.

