# 6.4 Participant Progress Definitions

Status	Treatment	Follow-Up		
Screen Failure	Participants from whom informed consent is obtained and is documented in writing (i.e., participant signs an informed consent form) but who is not entered into the study			
Completed Treatment / Completed FU*	Participants who complete the full course of IMPParticipants who complete all follow-u visits			
Completed Treatment / Discontinued FU	Participants who complete the full course of IMP	Participants who do not complete all applicable follow-up visits, regardless of the reason (excluding LTFU)		
Completed Treatment / Lost to Follow-Up	Participants who complete the full course of IMP	Participants who are unable to be contacted on or before their final visit		
Discontinued Treatment / Completed FU	Participants who discontinue treatment prior to completion of the protocol-defined treatment course	Participants who complete all applicable follow-up visits		
Discontinued Treatment / Discontinued FU**	Participants who discontinue treatment prior to completion of the protocol-defined treatment course	Participants who do not complete all applicable follow-up visits, regardless of the reason (excluding LTFU)		
Lost to Follow-Up	Participants who are unable to be contacted on or before their final treatment visit and it cannot be confirmed whether treatment was completed			

Table 2: Participant	Progress	Definitions
-----------------------------	----------	-------------

\* Note that this includes treatment failures who complete all applicable follow-up visits

\*\* Early Withdrawal

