8.1.2. The per-protocol (PP) population

The primary and secondary semen analyses will also be conducted on the PP population, defined as all participants who were enrolled and started treatment, excluding:

1. Participants not meeting the definition of having received an adequate amount of treatment.

2. Participants classified as major protocol deviations for analysis (see §7.4).

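### The SAP has no rule for semen values taken after a man starts another TB regimen; the exposed result is Week 44 recovery, not the Week 26 primary endpoint

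*SAP*

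**What the plan says.** **Semen analysis rule.** SAP 8.1.1 runs the primary and secondary semen analyses on every man who took a dose, and adds: "All data available will be considered for each time-point". SAP 7.6 specifies complete cases without imputation. SAP 7.5 aims to use scheduled and unscheduled data alike. SAP 9.2 gives descriptive summaries only.

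**Per-protocol set.** SAP 8.1.2 removes two groups. The first is "Participants not meeting the definition of having received an adequate amount of treatment", which SAP 7.3 sets at 146 of 182 doses within 238 days. The second is men with a major deviation under SAP 7.4. Starting another TB regimen after completing BPaMZ is not named in either.

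**Hormones.** SAP 8.1.1 names semen analyses only. The SAP states no rule on re-treatment for the hormone outcomes in Section 5.

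**Culture outcomes.** Here the SAP does deal with re-treatment. A favourable outcome requires no additional treatment (6.1), isolated positives are judged in men who have not been re-treated (7.2.2), and culture-negative status must be reached before re-treatment (7.2.3).

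**Who may stay in follow-up.** The footnote to Protocol Table 2 on men who finish treatment and follow-up reads: "Note that this includes treatment failures who complete all applicable follow-up visits". The sputum section of Protocol 1.1.1 refers to "a participant who withdrew and/or started re-treatment before the Week 78 visit", which does not equate re-treatment with withdrawal. Protocol 6.3 asks men taken off treatment to return for an early withdrawal visit and applicable follow-up visits. Its ban on other TB drugs is introduced by "The following medicinal products are prohibited from the Screening visit and during the treatment period", so it does not extend into follow-up.

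**The concern.** The primary objective concerns pretomanid within BPaMZ. Protocol 2.1 justifies the 18 weeks of follow-up after dosing as the period in which semen parameters could recover. Week 44 is the only scheduled semen time point in that period.

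Suppose a man finishes BPaMZ, starts a second TB regimen a few weeks later and still gives the Week 44 pair. Under SAP 8.1.1 his value enters the recovery summary unmarked. If the second regimen lowers his count, the summary shows a man who did not recover from BPaMZ. There is no control arm to reveal the difference. His Week 35 to 78 hormones can be misread in the same way.

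The protocol accepts in principle that a companion TB drug can confound this endpoint. It did not use BPaL for this study "as Linezolid has shown toxicity on testicular function in non-clinical studies".

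**Working it through.** **1. The plan's own figures reproduce.**
- Enrolment: 20 / (1 − 0.20) = 25.
- Treatment: 26 × 7 = 182 days; 146/182 = 80.2%; 182 + 56 = 238 days.
- Follow-up (Protocol 2.1): 75 + 37.5 + 10 = 122.5 days = 17.5 weeks, taken as 18.

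**2. When would a switch matter?** Inputs from Protocol 2.1 are a cycle of about 75 days and epididymal transit of about 10 days.
- One full cycle plus transit: 75 + 10 = 85 days = 85/7 = 12.1 weeks.
- Week 44 value: 44 − 12.1 = about Week 31.9. A switch before then puts a full cycle plus transit under the new regimen. A switch at Week 26 leaves 18 × 7 = 126 days, more than the 85 needed.
- Week 26 value: 26 − 12.1 = about Week 13.9. A man who switched that early would have stopped BPaMZ about halfway. He would usually have been withdrawn, and he could not have taken 146 doses: 13.9 × 7 is about 97 days.

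The exposure is therefore at Week 44. Week 26 is little affected.

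**3. Does the per-protocol set remove such a man?** Take a man who took all 182 doses on schedule and started another regimen at Week 30. He passes SAP 7.3 (182 ≥ 146, within 238 days). SAP 7.4 lists ineligible entry, withdrawal criteria met without withdrawal, and wrong treatment or dose. The second item might catch him if the review committee read it that way, but nothing requires it. By default he stays in both the ITT and PP summaries.

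**4. Size per man.** One man in 20 is 1/20 = 5 percentage points of the Week 44 proportion with at least a 50% decrease (SAP 5, item 3), if the second regimen carries him across that threshold. With all 25 enrolled men contributing, it is 1/25 = 4 points.

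**5. Chance of at least one such man.** The documents give no rate. Let p be the assumed share of men who start another regimen and remain in follow-up to give values. The chance is 1 − (1 − p)^n.

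| Assumed p | Expected men of 20 | Chance, n = 20 | Chance, n = 25 |
|---|---|---|---|
| 2% | 0.4 | 33% | 40% |
| 5% | 1.0 | 64% | 72% |
| 10% | 2.0 | 88% | 93% |

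These rates only illustrate the range. The true number may be zero.

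**The case against.** **Most re-treated men may leave the trial.** Protocol 6.3.4 describes withdrawal and referral to a local clinic for men who need further TB treatment, and Protocol 9.2 limits later collection for withdrawn men to SAEs. The re-treatment phrase in Protocol 1.1.1 belongs to a rule on which culture is tested for susceptibility. The Table 2 footnote mentions neither re-treatment nor semen. This stands: the documents permit the case but do not show it to be expected. A reader might take the roughly 90% favourable rate in Protocol 2.2.1.4 to mean one or two re-treated men by Week 44. That rate is for BPaL in highly resistant TB, and the protocol does not say that the remainder were re-treated.

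**Using all data can be a deliberate choice.** A treatment-policy summary is legitimate, and excluding values after re-treatment selects men on a post-baseline outcome. This stands, and is why the all-data summary should remain. However, the SAP does not say that it made this choice, and that summary alone cannot isolate recovery from BPaMZ.

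**The error described is a false alarm, not false reassurance.** This is fair if the second regimen is toxic, and it limits the severity. A wrong statement of non-recovery would still be a wrong safety conclusion.

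**The second regimen may not be toxic to the testis.** A reader might infer that it would contain linezolid. The documents say only that local guidelines apply, and the linezolid finding is non-clinical.

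**Hormone therapy.** A reader might also see a contradiction between the exclusion "Receiving any form of hormone or hormone-like (nutraceuticals) therapy, except for well treated hypothyroidism" and the Protocol 6.3 medication lists, which do not name such therapy. One is an entry criterion and the other a set of restrictions during the trial. They do not conflict, and nothing suggests that such use is likely.

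**Conclusion.** The gap is real but narrow. Followed as written, the SAP would count a semen value obtained under a second TB regimen as evidence on recovery from BPaMZ at Week 44, and it is equally silent on the Week 35 to 78 hormones. The PP analysis does not reliably remove such values. The documents do not support extending the point to the Week 26 primary endpoint.

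Each affected man would be up to 5 percentage points of a 20-man proportion. How many there will be is unknown and may be none; the 33% to 88% range rests on assumed rates of 2% to 10%. The Week 32 threshold rests on the protocol's approximate cycle and transit times. This is a cheap improvement to the plan, not a flaw in its main result.

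**What to change.** In SAP 8.1.1 and 9.2, before the Week 44 analysis:
- Keep the all-data summary.
- Add a pre-specified summary of Week 44 semen values and Week 35 to 78 hormone values that excludes those collected after the start of any other TB regimen. Start dates come from concomitant medications, which the Protocol 1.1.1 flow chart collects to Week 78.
- List the men affected, with the start date and regimen.
- Base the statement on recovery from BPaMZ on both summaries.

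The cost is a few lines of SAP text, one table and a short listing. No new data are needed. The added summary may hold one or two fewer men, and it describes only values not preceded by re-treatment, which its footnote should say.
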